5 STUDY DESIGN

5.1 Study description

PD0049 is a multicenter, open-label, two-arm, 12-week study in subjects with Parkinson's disease. On Day 1, eligible subjects will be randomized to either the Control Group or the Experimental Group in a 1:1 fashion. In both groups, subjects will use the Kinesia-ONE wearable device in-clinic at Visit 1 and Visit 2 for recording of specific motor symptoms, and subjects randomized to the Experimental Group will also use the Kinesia-360 wearable device at home while awake for continuous measurement of motor symptoms. The Investigator will use these symptom data to provide feedback to subjects on their motor symptoms and to supplement standard of care to titrate the optimal dose of Neupro for any given subject. In the Control Group, subjects will not use any wearable device at home, and the Investigator will use only standard of care to titrate the optimal Neupro dose.

Subjects in the Control Group and the Experimental Group will start treatment with Neupro 2mg/24h or 4mg/24h (at the Investigator's discretion and according to the disease stage of the subject) preferably on Day 1 (but no later than Day 4) or Day 4, respectively. Evaluations conclude 12 weeks after the start of treatment with Neupro (ie, at Visit 2).

The decision to prescribe Neupro must be made by the Investigator independent of his/her decision to include the subject in the study. The subject's treatment/Neupro intake must be within the terms of the marketing authorization; Neupro will not be supplied by UCB.

A schedule of study assessments is presented in [Table 5-1](#); for a detailed rationale of the study design see [Section 5.3](#).

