7.5 Randomization and numbering of subjects

Subjects will be randomized (1:1) to either the Control Group (without Kinesia-360 device to measure motor symptoms at home) or the Experimental Group (with Kinesia-360 device to measure motor symptoms at home) during the Screening Visit (Visit 1). The randomization will be stratified by site. A randomization list for each site with a block size of 4 will be provided to

the site. Each subject will receive a 5-digit number assigned at Screening that serves as the subject identifier throughout the study.

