8.1 Visit 1 /Screening

The Screening examinations will be completed within 4 days, the first of which will take place at the study site (in clinic) and will include the following:

Day 1, in clinic:

- Sign ICF
- Control Group and Experimental Group: Subject wears Kinesia-ONE sensor on the most affected side in the clinic to measure specific motor tasks in triplicate. Calculation of the average of triplicate resting tremor scores and triplicate finger-tapping speed scores (ie, 6 scores in total) must be >1.0 for subject inclusion in the study.
- Verification of inclusion/exclusion criteria and collection of demographic data (including weight and height)
- PDQ-39
- Investigator performs UPDRS assessment
- Patient Engagement Questionnaire
- Randomization (Control Group [without Kinesia-360 device use at home]/Experimental Group [with Kinesia-360 device use at home])
- Experimental Group: Trained in-clinic on Kinesia-360 device (and sent home with the device)
- Control Group: Start treatment with Neupro as prescribed (preferably on Day 1, but no later than Day 4); record date and dose
- Control Group and Experimental Group: Recording of AEs and concomitant medications

8.2 Week 1

Day 2 and 3, home:

- Experimental Group: Subject wears Kinesia-360 wrist and ankle devices on Days 2 and 3 at home for baseline
- Experimental Group: Recording of concomitant medications and Neupro dose via APP

Day 4, home:

- Experimental Group: Start treatment with Neupro as prescribed; record date and dose via APP

- Experimental Group: Recording of concomitant medications

8.3 Weeks 2, 3, and 4

Control Group, home:

- Investigator uses standard of care to adjust Neupro dose as needed.
- Phone contact initiated by subject or Investigator as needed. Documentation of any contact or dosage adjustment.

Experimental Group, home:

- Subject uses Kinesia-360 at least on 2 consecutive days at home weekly to measure motor symptoms.
- Subject accesses Kinesia-360 motor symptom reports on device following each day of measurements.
- Investigator receives Kinesia-360 motor symptom reports via web portal following each day of measurements.
- Investigator combines standard of care with weekly Kinesia-360 motor symptom reports to adjust Neupro dose as needed.
- Phone contact initiated by subject or Investigator as needed and dispatch of Kinesia-360 motor symptom reports. Documentation of any contact or dosage adjustment.
- Recording of concomitant medications and Neupro dose via APP.

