12.1 Definition of analysis sets

Four analysis sets will be defined for this study: the Enrolled Set (ES), the Safety Set (SS), the Full Analysis Set (FAS), and the Per-Protocol Set (PPS).

The ES will consist of all subjects who signed the ICF.

The SS will consist of all subjects who received at least 1 dose of Neupro. The SS will be used for the analysis of all demographic, disposition, and safety data.

The FAS will consist of all subjects who have at least 1 valid Baseline and at least 1 valid post-Baseline efficacy measurement. The FAS will be used for the analysis and presentation of the efficacy data. In the case of misallocation, subjects will be primarily analyzed according to Kinesia-360 application (yes/no). However, if applicable, sensitivity analysis will also be performed according to the randomized group.

The PPS will consist of those subjects in the FAS who do not have any important protocol deviations that would have an impact on the efficacy variables. The PPS will be used for sensitivity analysis.

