12.2 General statistical considerations

All analyses will be performed using SAS[®] version 9.3 or higher (SAS Institute, Cary, NC, USA). Continuous variables will be summarized by visit (where applicable) with the statistics including the number of subjects (n), mean, standard deviation (SD), median, minimum, and maximum. Categorical variables will be summarized by visit (where applicable) with frequency counts and percentages.

Unless otherwise specified, the comparisons will be for outcomes in subjects with Parkinson's disease in the Experimental Group (optimal Neupro dosing regimen will be titrated using motor symptom data collected with the Kinesia-360 wearable technology in addition to standard clinical practice) versus outcomes in subjects with Parkinson's disease in the Control Group (optimal Neupro dosing regimen will be titrated using only standard clinical practice). It is obvious that Kinesia-360 based efficacy data will be presented for the Experimental group only.

Unless otherwise specified, the level of significance for all tests will be 0.05. All statistical tests are 2-sided; however, they are exploratory only and p-values <0.05 do not indicate statistical significance, since no alpha adjustment will be performed.

All data recorded in the eCRF, APP, and questionnaires will be listed.

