### **3.5.3 Full Analysis Set**

The FAS will consist of all subjects who have at least 1 valid Baseline and at least 1 valid post Baseline efficacy measurement. That means, subjects in FAS have non-missing values at Visit 1

and at Visit 2 either for the UPDRS Part III Motor Score or for at least one Kinesia-ONE variable or for Neupro dose per 24h.

The FAS will be used for the analysis and presentation of the efficacy data. In the case of misallocation, subjects will primarily be analyzed according to Kinesia-360 application (yes/no). However, if applicable, sensitivity analysis will also be performed according to the randomized group.

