## **4.5 Multiple comparisons/multiplicity**

All statistical tests are considered exploratory, and calculated p-values  $<0.05$  do not indicate statistical significance, since no alpha adjustment will be performed.

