### **8.1.4 Supportive and sensitivity analyses of the primary efficacy variables**

The primary analyses (ANCOVA and corresponding summary statistics) will be repeated for the PPS on observed cases.

In case of misallocation to treatment groups, the primary analyses will be repeated for the FAS as randomized.

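### For misallocated subjects, efficacy is grouped primarily by Kinesia-360 use and only secondarily as randomised; the order should be reversed (minor).

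*SAP*

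**What the plan says.** Three places set the rule, and they agree.

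- Protocol 12.1, in the Full Analysis Set definition: "subjects will be primarily analyzed according to Kinesia-360 application (yes/no". A sensitivity analysis by randomised group follows, if applicable.
- SAP 3.5.3 repeats this: "In the case of misallocation, subjects will primarily be analyzed according to Kinesia-360 application (yes/no". Randomised group is again the sensitivity grouping, if applicable.
- SAP 8.1.4, on supportive and sensitivity analyses: "In case of misallocation to treatment groups, the primary analyses will be repeated for the FAS as randomized".

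SAP 4.6 names the FAS as the primary set for efficacy, so the device-use grouping carries into the primary estimates. No section makes the randomised grouping primary for efficacy. Safety goes the other way: SAP 10 analyses the Safety Set, in general, as randomised.

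**The concern.** Randomisation ensures that the two groups differ only by chance when the device has no effect. That holds only while subjects are counted in the group to which they were randomised. Once a subject is counted by the device actually used, whatever caused the wrong allocation can enter the comparison.

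Two design features make the protection worth keeping. Protocol 5.1 describes a "multicenter, open-label, two-arm, 12-week study", and under protocol 7.5 "A randomization list for each site" is provided to the site. A departure from allocation therefore cannot simply be assumed to be unrelated to the subject's condition.

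There is also a consistency problem. A misallocated subject could be in one group in the efficacy tables and in the other in the safety tables. Neupro discontinuation shows this most clearly. It is a primary efficacy variable in SAP 2.2.1.1 and a safety variable in SAP 10.4.2, which refers back to SAP 8.1.2. Its grouping for a misallocated subject is unclear.

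**Working it through.** The documents state no effect size, SD or power, so there is no figure of the plan's own to reproduce. The rule itself is established by the sections cited above. What follows only illustrates its possible size.

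**From the documents:** 20 subjects per group and about 6 sites (protocol 5.1.2); ANCOVA with baseline, center and group (SAP 8.1.2); two-sided 95% confidence intervals.

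**Assumed:** no device effect; in each group, m = 1 or 2 subjects have a change score d = 0.5 or 1 SD worse than the rest. The unit is the residual SD, so the gap d must remain after adjustment for baseline and center, which is a strong assumption.

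**Yardstick.** Residual df = 40 − 1 (intercept) − 1 (group) − 1 (baseline) − 5 (center) = 32. Half-width of the 95% CI = t(0.975, 32) × √(2/20) = 2.037 × 0.316 = 0.644 SD. With groups of 18 and 22 it is 0.647.

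**A. One-way regrouping.** The m worse Experimental subjects are counted as Control. The Experimental mean becomes 0. Control then has 20 + m subjects, 2m of them worse, so its mean is −2md/(20 + m). False difference = 2md/(20 + m).

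**B. Exchange of m subjects of equal prognosis in each direction.** False difference = 0.

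**C. Exchange of the m worse Experimental subjects for m typical Control subjects.** False difference = 2md/20.

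| m | d | A (SD) | A / 0.644 | C (SD) | C / 0.644 |
|---|---|---|---|---|---|
| 1 | 0.5 | 0.048 | 7% | 0.050 | 8% |
| 1 | 1 | 0.095 | 15% | 0.100 | 16% |
| 2 | 0.5 | 0.091 | 14% | 0.100 | 16% |
| 2 | 1 | 0.182 | 28% | 0.200 | 31% |

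With d = 0 every entry is 0. A simulation of random one-way regrouping (40,000 runs) gave mean false differences of 0.002 (m = 1) and 0.000 (m = 2). Under the randomised grouping the expected false difference is 0 for every m and d.

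**What the randomised grouping costs.** If the device has a true effect, one-way misallocation leaves (20 − m)/20 of it, a dilution of m/20 = 5% or 10%. An exchange leaves (20 − m)/20 − m/20, a dilution of 2m/20 = 10% or 20%.

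**The case against.** The strongest reply is that the rule may never operate. It applies only if there is misallocation, and neither document reports any. SAP Amendment 1 was written after the Data Evaluation Meeting. It added handling for irregularities that did arise, such as a rescreened subject and Neupro taken after screen failure, and it edited SAP 3.5.2 but left 3.5.3 alone. That suggests there was no misallocation, without proving it. The calling of one grouping primary also triggers no decision. Protocol 12.2 says of the tests that "they are exploratory only and p-values <0.05 do not indicate statistical significance", SAP 4.5 says "All statistical tests are considered exploratory", and the as-randomised repeat of the primary ANCOVAs is already prespecified. Grouping by use also avoids dilution of a true device effect. All of this stands, and it is why the point is minor. It does not show that the device-use estimate should come first when the two differ.

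Three stronger readings are tempting, but the documents do not support them.

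- *That the trial's results are biased.* No misallocation is reported, and even if some occurred, clerical errors would give no expected bias.
- *That Experimental subjects who stop wearing the device move to Control.* SAP 8.1.4 speaks of misallocation to treatment groups, which reads as a wrong assignment. Protocol 8.2 also has this step: "Subject wears Kinesia-360 wrist and ankle devices on Days 2 and 3 at home for baseline". That comes before Neupro starts on Day 4, so at most a subject who never wore the device could be regrouped for non-wear.
- *That the randomised analysis is missing.* It is demoted, not omitted. The real gap is narrower. SAP 8.1.4 describes the primary analyses as ANCOVA with summary statistics. Read literally, that leaves out the discontinuation logistic regression, and it does not reach PDQ-39, PAM-13 or UPDRS Part II. For those, the as-randomised result rests on the unspecific sentence in SAP 3.5.3.

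**Conclusion.** The point holds and is minor. If misallocation occurs, the plan makes a grouping not protected by randomisation the primary one for efficacy, while safety is in general analysed as randomised. The order should be reversed. The effect is nil without misallocation. The illustrated 0.05 to 0.20 SD rests entirely on the assumed numbers of subjects and prognosis gaps, neither of which the documents supply. Even the largest illustrated value is under a third of the CI half-width.

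**What to change.** - **SAP 3.5.3.** Replace the misallocation rule with wording such as: *Between-group efficacy comparisons on the FAS and the PPS, including the logistic regression of Neupro discontinuation, use the randomized group as the primary grouping. If any subject is misallocated, they are repeated by Kinesia-360 application (yes/no) as a sensitivity analysis. Kinesia-360 scores remain descriptive, for subjects who used the device.* The limit to between-group comparisons is needed because Kinesia-360 scores are also listed as efficacy variables but have no Control counterpart.
- **SAP 8.1.4.** In case of misallocation, repeat the primary analyses, including the discontinuation regression, by Kinesia-360 application.
- **SAP 10.4.2.** State that the same randomised grouping applies where discontinuation is reported as a safety variable, in agreement with SAP 10.
- **SAP 3.9.** Record the departure from protocol 12.1 with a date and reason; the section now lists only the additional Kinesia-ONE scores. Protocol 13.5 requires an amendment for significant protocol changes, so the sponsor must decide whether this entry is enough. If group results have already been seen, report both groupings side by side.

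No new data are needed. The ANCOVAs of the primary variables swap roles. A little extra programming is needed for the discontinuation model and for the variables outside SAP 8.1.4 (PDQ-39, PAM-13, UPDRS Part II). The statistical cost is the dilution worked out above, which the retained device-use analysis would help to show.

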#### **3.5.4 Per Protocol Set**

The PPS will consist of those subjects in the FAS who do not have any important protocol deviations that would have an impact on the primary efficacy variables. The PPS will be used for sensitivity analysis.

### **3.6 Treatment assignment and treatment groups**

Eligible Subjects will be randomized to either the Control Group or the Experimental Group. In the Control Group, optimal Neupro dosing regimen will be titrated using standard clinical practice only. In the Experimental Group, optimal Neupro dosing regimen will be titrated using motor symptom data collected with the Kinesia-360 wearable technology in addition to standard clinical practice.

Comparisons between Control Group and Experimental Group will be performed for outcomes where data are available for both groups, e.g. Kinesia-ONE data, and questionnaires. Kinesia-360 data however are only available for subjects in the Experimental Group, and will therefore be presented only for this group.

#### **3.7 Center pooling strategy**

No pooling of centers is planned for this study.

#### **3.8 Coding dictionaries**

All AEs will be coded for analysis according to the Medical Dictionary for Regulatory Activities (MedDRA)® coding dictionary, using the latest version available. Prior and concomitant medications will be coded for analysis using the latest version of the World Health Organization Drug dictionary (WHO-DD).

#### **3.9 Changes to protocol-defined analyses**

Additional Kinesia-ONE scores which were not prespecified in the clinical study protocol are provided by the vendor. These will be analyzed in the same way as the prespecified variables.

### **4 STATISTICAL/ANALYTICAL ISSUES**

#### **4.1 Adjustments for covariates**

The continuous efficacy variables, change from Baseline to Visit 2 (for all efficacy variables not based on Kinesia-360) will be analyzed utilizing an analysis of covariance (ANCOVA) with Baseline as a covariate, “center” as factor, and “group” as main factor. The adjustments for baseline value and center are included, as these variables may have a systematic impact on the efficacy outcome.

## **4.2 Handling of dropouts or missing data**

Subjects who prematurely discontinue the study will be evaluated based on the data collected at the Withdrawal Visit. The Withdrawal Visit data will be used similar to Visit 2 data.

Adverse events with missing intensity will be assumed to be severe. Adverse events with missing relationship to study medication per the investigator will be assumed to be related.

For analyses of AEs and concomitant medication usage, a complete date must be established in order to correctly identify the AE or medication as occurring during treatment or not. For purposes of imputing missing components of partially-reported start and stop dates for AEs and for medication use, the algorithms listed below will be followed. Start and stop dates of AEs or concomitant medication will be displayed as reported in the subject data listings (i.e., no imputed values will be displayed in data listings).

- Missing start day, but month and year present: If the start of study medication occurred in the same month and year as the occurrence of the AE/concomitant medication, the start day of the event/concomitant medication will be assigned to the day of first application of study medication. Otherwise the start day will be set to the 1st day of the month.
- Missing start day and month, but year present: If the start of study medication occurred in the same year as the occurrence of the AE/concomitant medication, the start day and month will be assigned to the date of first application of study medication. Otherwise the start day and month will be set to January 1st.
- Missing end day, but month and year present: The end day will be set to the last day of the month.
- Missing end day and month, but year present: If the maximum of the subject's date of study termination or the date equivalent to 30 days after the subject's last application of study medication is the same year as the occurrence of the AE/Concomitant medication, then the end day and month will be set to the maximum of the date of study termination or the date equivalent to 30 days after last application of study medication. Otherwise the end day will be set to December 31st of the given year.

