### 6.4 Prior and concomitant medications

Medications will be considered as prior if the start date of the medication is before the date of first patch administration. Medications will be considered as concomitant if they are taken at least once in the treatment period starting with the first patch administration and ending after the last patch administration during the study. Medications starting prior to first patch administration and continuing into the treatment period will be considered both prior and concomitant medication.

In case of partial or missing dates the rules described in [Section 4.2](#) will be applied.

Prior and concomitant medications will be summarized separately for the SS. The number and percentage of subjects who used prior and concomitant medications, respectively, will be presented according to the anatomical main group (level 1), the pharmacological subgroup (level 3), and the preferred term.

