### **10.2 Adverse events**

Adverse events with start date prior to first administration of study medication are defined as pre-treatment AEs. No summaries of these events will be provided, they are included in listings.

Treatment emergent AEs are all AEs starting on or after the date of first study medication and up to 30 days after the last dose of study medication. Also AEs with an earlier onset are treatment emergent, if the intensity worsened during the treatment period. AEs occurring more than 30 days after the last dose will not be considered treatment emergent.

For AEs with a partial start date, the imputation rules as described in [Section 4.2](#) will be applied. If a start date is completely missing, then the AE will be considered treatment-emergent unless the AE end date is on or before the first date of study medication. Duration should not be calculated if there is missing stop date information.

Treatment emergent adverse events (TEAE) will be tabulated by MedDRA system organ class (SOC), high level term (HLT) and preferred term (PT). The number and percentage of subjects experiencing each event at least once will be summarized in addition to the number of events. In summaries of TEAEs by relationship and intensity, respectively, the number of events will not be presented.

All summaries will be sorted alphabetically by SOC and HLT and by descending frequency of PT in the Experimental Group within HLTs. If there is more than one PT with the same frequency in the Experimental Group these events will be sorted alphabetically.

Tables showing TEAEs, serious TEAEs, non-serious TEAEs, TEAEs leading to discontinuation of study medication, TEAEs by maximum intensity, TEAEs by maximum relationship, and TEAEs including subject numbers will be provided. The table showing AEs leading to study discontinuation will also be provided for the ES. A glossary of MedDRA terms and associated investigator provided terms for all adverse events will be presented. Individual subject data listings will be presented for all AEs, serious TEAEs, TEAEs leading to withdrawal of study medication, and TEAEs with fatal outcome.

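### SAP 4.2 moves a partial start date to the first-patch day without looking at the end date, so AEs and medications known to have ended before Neupro are misclassified

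*SAP*

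**What the plan says.** SAP 4.2 gives the purpose of date imputation: "a complete date must be established in order to correctly identify the AE or medication as occurring during treatment or not". It then sets two rules for partial start dates.

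- **Day missing.** If Neupro began in the same month and year, "the start day of the event/concomitant medication will be assigned to the day of first application of study medication". If not, "Otherwise the start day will be set to the 1st day of the month".
- **Day and month missing.** If Neupro began in the same year, "the start day and month will be assigned to the date of first application of study medication". If not, January 1st is used.

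Two other sections rely on these rules.

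- **SAP 10.2 (AEs).** The definition goes by start date: "Treatment emergent AEs are all AEs starting on or after the date of first study medication and up to 30 days after the last dose". For incomplete starts it points back to SAP 4.2: "For AEs with a partial start date, the imputation rules as described in" that section apply. Only when the start is completely missing is the end date consulted: the AE counts as treatment-emergent "unless the AE end date is on or before the first date of study medication".
- **SAP 6.4 (medications).** "Medications will be considered as prior if the start date of the medication is before the date of first patch administration". A medication is concomitant if it was taken at least once in the treatment period. Partial dates again go to SAP 4.2.

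**The concern.** Moving a start date to first dose is reasonable when the timing is unclear. If the reported end date is before the first patch, the timing is not unclear: the event or the drug was over before Neupro. The rule then assigns a start later than the end and classifies the record from that start, which defeats the purpose SAP 4.2 states.

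It also makes the SAP inconsistent with itself, because an AE with a known start month is classified less accurately than one with no start date.

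At stake are the TEAE counts and the prior and concomitant medication tables. The medication tables carry some weight here because SAP 6.3 states that medical history and concomitant diseases are not collected.

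**Working it through.** The documents give no figure to reproduce, so the check applies the written rules to example records. **Assumed dates:** first patch 15 June 2017, last patch 5 September 2017.

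**Rules applied as written**

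1. Imputed start = first-patch date if the known month and year (or the year alone) match; otherwise the 1st of the month or January 1st (SAP 4.2).
2. TEAE if first patch ≤ start ≤ last dose + 30 days. If the start is completely missing, TEAE unless end ≤ first patch (SAP 10.2).
3. Prior if start < first patch. Concomitant if taken on or after the first patch within the treatment period (SAP 6.4).

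| Record | Reported start | Reported end | Imputed start | Class as written |
|---|---|---|---|---|
| AE | June 2017 | 14 June 2017 | 15 June 2017 | TEAE; start one day after end |
| AE | 2017 | 14 June 2017 | 15 June 2017 | TEAE; start one day after end |
| AE | missing | 14 June 2017 | none | not a TEAE |
| Medication | June 2017 | 10 June 2017 | 15 June 2017 | neither prior nor concomitant |
| Medication | 2017 | 20 March 2017 | 15 June 2017 | neither prior nor concomitant |
| Medication | 2017 | ongoing | 15 June 2017 | concomitant only |
| Medication | May 2017 | 10 June 2017 | 1 May 2017 | prior (correct) |
| Medication | 2016 | ongoing | 1 January 2016 | prior and concomitant (correct) |

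The first three rows describe an AE with the same end date and differ only in how much of the start is known. The AE is excluded only when nothing is known. The two stopped drugs fail the prior test because of the imputed start, and fail the concomitant test because they were not taken in the treatment period.

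**The same records with an end-date check.** If the end is before the first patch, the imputed start may not be later than the end. Both partial-start AEs get 14 June and are not TEAEs. The two stopped drugs get 10 June and 20 March and are prior only. The other rows do not change.

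**How many AEs can be exposed.** AEs are collected from consent (Protocol 10.1.1.1), which is on Day 1 (Protocol 8.1). Pre-Neupro days on study = day of first patch − 1:

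- Experimental Group, Day 4 start: 4 − 1 = 3 days.
- Control Group, Day 1 start as preferred: 1 − 1 = 0 days; latest permitted start, Day 4: 4 − 1 = 3 days.

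A falsely treatment-emergent AE must therefore begin and end within Days 1 to 3, and have a known end date but an incomplete start, among about 40 subjects.

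**The case against.** The best defence is that moving an ambiguous start to first dose is a usual conservative convention. It fits the same section's treatment of missing intensity as severe and missing relationship as related. That stands where the end date is unknown or falls on or after the first patch. It does not cover an end date known to be earlier, and SAP 10.2 already makes that distinction for completely missing starts.

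Several stronger readings are tempting, but the documents do not support them.

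- **That SAP 10.2 is also wrong to exclude a missing-start AE ending on the first-patch day.** Such an AE is treatment-emergent only if it also began that day or worsened on treatment. Excluding it is a defensible boundary choice, and including it would bring in AEs that began on Days 1 to 3.
- **That the rule biases the group comparison of TEAEs.** The fixed three-day stretch is in the Experimental Group, but Control may also start as late as Day 4, and no document shows an affected record. Most Day 1 to 3 dates do share a month with Day 4 (over 2017, 1 − 72/1095 = 0.934). That says how often the months match, not how many AEs are misclassified.
- **That every drug begun in the year of first patch with an unknown month is affected.** A drug begun after the first patch stays correctly concomitant.
- **That background Parkinson's therapy is misstated.** A drug ongoing at the first patch stays in the concomitant table and loses only its prior label. Drugs begun in an earlier year are classified correctly. The documents describe no look-back for drugs already stopped, so the frequency of lost records cannot be judged.
- **That negative durations will be reported.** SAP 4.2 keeps imputed dates out of the listings, and nothing says durations use them.

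**Conclusion.** The point holds as a narrow error in a stated rule. With a partial start matching the month and year (or year alone) of first patch, and an end date before the first patch, SAP 4.2 produces a false TEAE, or removes a medication from both the prior and the concomitant table. No other section restores the missing check.

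It is a minor point. Few AEs can be affected; the number of medication records is not known from the documents; no efficacy analysis changes. The conclusion rests on the text of SAP 4.2, 6.4 and 10.2. The example dates are assumptions and affect only the illustration.

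**What to change.** Add to both start-date bullets in SAP 4.2:

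- The first-patch date is used only if the reported or imputed end date is missing or not before the first patch.
- Otherwise the record is classed as pre-treatment (AE) or prior (medication). Its imputed start may not be later than its end date and, for an AE, may not be earlier than consent.

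The consent limit is needed because falling back to the 1st of the month or January 1st can put an AE before its collection began. In the example, a Day 4 patch on 15 June puts Day 1 on 12 June, so 1 June would be too early. SAP 10.2 needs no change.

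The cost is a short addition to the SAP and a few lines of program code, using dates already collected. Ongoing drugs with a partial start will still be shown as concomitant only, which this check is not meant to alter.
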